Initial assessments will be conducted in the few weeks preceding patients' already-scheduled appointments for dental treatment at TUKSoD. Patients meeting inclusion and exclusion criteria will then be offered I-CBT or the control intervention, to occur immediately prior to their scheduled dental treatment appointment. Efficacy based on primary outcome measures (e.g., reduction from baseline on self-rated and clinician-rated measures of dental anxiety/fear) and secondary outcome measures will be examined at assessments one and three months thereafter. Some additional interview ratings will be gathered from patients after they complete the dental anxiety intervention and after they complete the pursuant dental treatment appointment, and one brief questionnaire will be administered six and twelve months later. Finally, we will examine the impact that the intervention may have on attendance at scheduled dental appointments over the next 12 months.

2) Protocol Title

Efficacy of an Internet-based intervention for dental anxiety

3) Investigators

Page 1 of 28 Revision: May 12, 2023

[name], Associate Professor, Chair, and Residency Director, Pediatric Dentistry and Community Oral Health Sciences, Maurice H. Kornberg School of Dentistry, Temple University

[name], Assistant Professor, Department of Oral Health Sciences, Maurice H. Kornberg School of Dentistry, Temple University

4) Objectives

The primary goal of human subjects activities described in this protocol is to evaluate the efficacy of the Internet-based intervention for dental anxiety among patients presenting to the participating clinic(s). To achieve this overall goal, we propose 3 primary objectives:

Objective 1: We will compare the efficacy of I-CBT as administered by personnel with training and experience in CBT to the efficacy of the intervention as administered by dental assistants who have undergone a brief but specific training in the administration of the intervention, a goal which would allow the greater dissemination of this intervention. We will also examine within-group reduction of anxiety at assessments one and three months after the administration of the intervention.

Objective 2: We will compare the efficacy of the intervention, administered either by CBT personnel or dental staff, to an active control condition, the viewing of the control video and the notification of the dental provider of the patient's score on a measure of dental anxiety before the dental appointment.

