We propose general statistical analyses and sample size considerations for the U01 trial. Initial analyses will be conducted to determine normality of distributions of the continuous variables, and any necessary transformations will be conducted. Primary outcomes will be the MDAS (score ranging from 5 to 25) and the rating of fear of dental procedures from the ADIS-5 (0=no fear to 8=very severe fear). All eligible patients will be randomly assigned to one of the three conditions described above. Although randomization should provide relatively comparable groups, demographic variables that differ between groups and are correlated with the primary outcomes will be used as covariates. Patients will receive a full battery assessment of outcome measures at baseline and 1 and 3 months after the day of their index dental appointment (as well as assessments on the day of their index dental appointment).

Page 16 of 28 Revision: May 12, 2023

Preliminary statistical analysis will include measures of central tendency and dispersion, as well as an examination of the bivariate relationships among the primary and secondary outcome variables (e.g., client satisfaction, blood-injury-injection phobia), potential moderators (e.g., distress tolerance and pain sensitivity), and demographic characteristics.

Differences between the groups on baseline demographic, clinical and psychological measures will be examined using χ^2 (Pearson) or Student's *t*-tests, as appropriate. Moreover, differences on the variables listed above among completers and drop-outs will also be explored. Both per protocol and intention to treat (ITT) analyses will then be conducted.

Specific Aim 1

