Aim 1 will test the equivalence hypothesis (Ho: the two intervention conditions are not equivalent). MDAS and ADIS fear scores will be the primary outcomes to be compared between two intervention conditions for equivalence. The two one-sided tests (TOST) procedure of Schuirmann (1987) will be used to conduct the equivalence test. Linear mixed-effects models for repeated measures will be used to assess differences between intervention groups using the MDAS and ADIS fear rating as continuous outcome variables. Linear mixed-effects models will also investigate the treatment effect on dental anxiety or fear after accounting for other confounding factors. Similar analyses will be conducted for secondary outcome measures (pain sensitivity index, anxiety sensitivity index, sleep disturbance and sleep-related impairment scales, disability scale, distress tolerance scale, client satisfaction and blood-injury-injection phobia). Statistical significance will be set at p < 0.05. Multiple imputation (MI) will be used to handle missing follow-up data as described below.

Aim 1 will also determine whether the Internet-based intervention reduces dental anxiety/fear as determined by self-ratings or assessor ratings at one month and three months post-intervention. Initially, we will assess within-group change of anxiety or fear scores for each condition separately using paired *t*-tests. Linear mixed-effects models will be used to estimate within-group reduction of anxiety/fear at assessments one and three months after the administration of the intervention adjusting for other covariates.

Specific Aim 2

Aim 2 will assess the superiority hypothesis (Ho: there are no significant differences between the interventions and control). MDAS and ADIS-5 fear scores will be the primary outcomes to be compared. Initially, we will assess the differences between the interventions and control using two-sample *t*-tests. The main analysis will be based on linear mixed-effects models for repeated measures (using the MDAS score and ADIS-5 fear rating as continuous outcome variables) to assess differences between intervention and control groups. Linear mixed models will also investigate the treatment effect on dental anxiety or fear after accounting for other confounding factors. Similar analyses will be conducted for secondary outcome measures (e.g., client satisfaction and blood-

Page 17 of 28 Revision: May 12, 2023

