injury-injection phobia). Statistical significance will be set at p < .05. MI will be used to handle missing follow-up data as described below.

Specific Aim 3

Aim 3 examines the impact of the intervention on attendance at scheduled dental appointments over the following 12-month period to determine whether the intervention affects avoidance of dental procedures. First, we will examine whether the overall attendance rate is changed from pre- to post-intervention using a one-sample Chisquare test comparing the 12-month periods immediately before and immediately after the delivery of the intervention. The two intervention groups combined will be used for this analysis. We will also use a Chi-square test to compare post-intervention attendance rates between the two intervention groups. We expect the attendance rates will be similar for the two groups. Finally, we will conduct logistic regression analyses predicting attendance/nonattendance among intervention patients who did or did not demonstrate reduction in dental anxiety at 3-month follow-up. Relevant demographic characteristics and other potential confounding variables or moderators will be included in the final logistic models.

Missing Data

MI will be used to handle missing follow-up data when conducting ITT analysis for Specific Aims 1 and 2. There will be three steps in the MI procedure: 1) The missing follow-up data will be filled in 100 times to generate 100 complete datasets; 2) The 100 datasets will be analyzed by analyses of covariance with follow up scores at 1-month or 3-month as outcomes and treatment groups as the independent variable (Tr1 vs. Tr2 for Specific Aim 1, or Tr1 + Tr2 vs. AC for Specific Aim 2), controlling for baseline scores; 3) The results from the 100 complete datasets will be combined for the MI inference (Rubin 1987). SAS PROC MI and PROC MIANALYZE will be used for multiple imputation analysis using SAS 9.4 (SAS Institute Inc., Cary, NC, USA).

Analysis of Secondary Objectives

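### Aim 2 tests two primary outcomes, each at p < .05, without naming a deciding visit or contrast, an either/both rule or an alpha split, so 5% is not the error rate of its conclusion if either outcome can count as success.

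*Combined protocol and SAP*

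**What the plan says.** - **Outcomes.** Planned Analyses: "Primary outcomes will be the MDAS (score ranging from 5 to 25) and the rating of fear of dental procedures from the ADIS-5". Specific Aim 2 repeats this: "MDAS and ADIS-5 fear scores will be the primary outcomes to be compared".
- **Time points.** The Abstract says of efficacy that primary and "secondary outcome measures will be examined at assessments one and three months thereafter". Neither visit is called primary.
- **Threshold.** Specific Aim 1: "Statistical significance will be set at p < 0.05". Specific Aim 2: "Statistical significance will be set at p < .05".
- **Model for Aim 2.** Two-sample t-tests come first as an initial step, then "The main analysis will be based on linear mixed-effects models for repeated measures". Whether the group effect is tested at each visit or over both is not stated.
- **ITT with missing data.** The Missing Data section describes a different model, "analyses of covariance with follow up scores at 1-month or 3-month as outcomes", adjusted for baseline. For Aim 2 it compares the two I-CBT arms pooled against control.
- **Analysis sets.** "Both per protocol and intention to treat (ITT) analyses will then be conducted". Neither is named as deciding.

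None of these sections gives a testing order, an either/both rule or a multiplicity adjustment.

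**The concern.** A threshold of .05 controls the error of one test. The Aim 2 conclusion, that I-CBT does better than the active control, may rest on more than one. With two primary outcomes there are at least two tests. If each visit is tested separately, as in the imputation step, there are four. When any one of them may carry the claim, the error of the conclusion exceeds the stated level.

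The practical stake is a split result. If the MDAS separates the groups and ADIS-5 fear does not, or the effect shows at 1 month but not at 3, the plan does not say whether the trial has succeeded, and the reading would be chosen after the data are seen. Aim 1 has the same gap: equivalence could be met on one outcome or visit and missed on another, and that claim is meant to support delivery by dental assistants.

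**Working it through.** The plan states no overall error rate, so there is no figure of its own to reproduce; .05 is an input.

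**Inputs from the documents:** two primary outcomes; two follow-up visits; .05 per test; one pooled comparison in Aim 2, so the number of arms adds no further tests; 550 patients in three roughly equal arms, which gives about 367 pooled I-CBT against 183 control.

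**Assumptions:** two-sided tests (inferred from the null of no difference); success on any one test suffices; correlation between outcomes .4-.7 and between visits .6-.8.

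**1. Independent tests (upper reference).** Chance of at least one false result among k tests = 1 − (1 − .05)^k.
- k = 2: 1 − .95² = 9.75%.
- k = 4: 1 − .95⁴ = 18.5%.

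**2. Correlated tests.** Multivariate normal test statistics under no effect were simulated (2,000,000 draws), counting draws in which at least one |Z| exceeds 1.96. For four tests, the correlation between different outcomes at different visits is the product of the two correlations.

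| Tests | Correlation: outcomes / visits | Any false result | False result favouring I-CBT |
|---|---|---|---|
| 1 | – | 5% | 2.5% |
| 2 | .4 / – | 9.3% | 4.7% |
| 2 | .7 / – | 8.3% | 4.2% |
| 4 | .4 / .6 | 16.0% | 8.0% |
| 4 | .5 / .7 | 14.8% | 7.4% |
| 4 | .7 / .8 | 12.8% | 6.4% |

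The last column counts only Z > 1.96.

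**3. Both outcomes required on one contrast.** Under no effect on either outcome, both are significant in 0.2% of draws at correlation 0 and 2.2% at .8. The rate cannot exceed 5%, so this rule needs no alpha split.

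**4. Power cost of Holm.** Assume d = 0.3 and no attrition. The expected test statistic is 0.3 / √(1/367 + 1/183) = 3.315.
- At two-sided .05 (critical value 1.960): power 91.2%.
- At two-sided .025 (critical value 2.241): power 85.9%.
- Under Holm, once one outcome passes at .025 the other is tested at .05. If both outcomes have d = 0.3, simulated power per outcome is 90.5% at correlation 0 and 88.9% at .8, a loss of about 1-2 points.
- If only one outcome has an effect, its power is about 86%, a loss of about 5 points.

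**The case against.** Much can be said for the plan. It does name a main analysis for Aim 2, so a reader who infers that the t-test, the mixed model and the imputation ANCOVA are equal routes to success goes too far: the t-tests are introduced as an initial step. The main model may give one overall group effect per outcome, and therefore two tests. Separate 1- and 3-month tests between the groups are explicit only in the imputation step. The plan never says that one significant outcome is enough, and if both were required on one contrast there would be no inflation.

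A reader might also infer that the chance of a false efficacy claim is 13-16%. The documents do not support that as a flat statement. It needs four tests, any one counting, assumed correlations, and the inclusion of results in which I-CBT does worse than control. Such results cannot support a claim that it works, and without them the figure is about half.

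These points reduce the size of the problem and make it conditional. They do not remove it. Naming the mixed model leaves its contrast open. The specified ITT method uses a different model from the main analysis. Silence on an either/both rule excludes neither reading. Even in the mildest either-outcome case, one contrast per outcome, the error in favour of I-CBT is about 4-5% rather than 2.5%.

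**Conclusion.** The concern holds in conditional form. As written, the plan does not hold the error of the Aim 2 conclusion at 5%, because it does not define what counts as success on two primary outcomes. If either outcome suffices, the two-sided error is about 8-10% with one mixed-model contrast per outcome. It is about 13-16% if any of four outcome-by-visit tests counts, with 18.5% under independence. In favour of I-CBT only, the figures are about 4-5% and 6-8%, against 2.5%. The per-protocol and covariate-adjusted analyses are further looks that these figures do not count.

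For Aim 1 the same rule is missing, but no error rate was computed for the equivalence tests, so none of these percentages applies there. The point should be settled before the analysis; it does not call the design or the data collection into question.

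**What to change.** Add a paragraph to Planned Analyses:

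1. **One deciding contrast.** Within the mixed model already named for Aim 2, pre-specify one contrast in the ITT set, for example the group difference at 3 months or the average over 1 and 3 months. The choice is the sponsor's. State how missing data are handled in that model, since the imputation step is now tied to a different one.
2. **Aim 2.** Apply Holm across MDAS and ADIS-5 fear: the smaller p-value is tested at .025 and, if it passes, the other at .05.
3. **Aim 1.** Claim equivalence only if both outcomes pass TOST on the same type of contrast between the two I-CBT arms. This needs no alpha split.
4. **Supportive results.** Label any other visit-specific contrasts, the t-tests, the imputation ANCOVA and the per-protocol results as supportive.

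**Cost.** No change to sample size or data collection. At 367 vs 183 with no attrition and an assumed d = 0.3, Holm costs about 1-2 points of power per outcome if both outcomes have that effect, and at most about 5 points (91% to 86%) if only one does. Requiring both outcomes in Aim 1 lowers power for the equivalence claim, by an amount not computed here.

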Time 5 is the follow-up contact three months (12-15 weeks) after the day of the dental anxiety intervention and the scheduled dental appointment. The full list of assessments administered at the pre-intervention assessment session will be re-administered. This includes the ADIS-5 interview, amended to include some debriefing questions as described above, and all questionnaires including the CSQ-8. This session will be scheduled as an in-person visit, with both interview and questionnaires completed in the research offices. However, if logistical barriers or scheduling difficulties arise, the session may be conducted by telephone. In that circumstance, questionnaires may be administered over the phone or online. This assessment is identical to the one at Time 4. Brief (5-item) assessments will also be conducted by phone or online at 6- and 12-month follow-ups. Attendance at dental appointments will continue to be monitored until 12 months have passed since the day of the dental anxiety intervention.

Study Procedures/Evaluations

A table is provided below which lists the measures to be administered and the timing of their administration:

Table 1. Measures and Timing of Their Administration

Measure	Initial	Baseline	Dental	1-mo	3-mo	6-mo	12-mo
	Screen	Assess-	Anxiety	Follow-	Follow-	Follow-	Follow-
		ment	Intervention/	up	up	up	up
			Index Dental				
			Appointment				
Modified Dental Anxiety Scale	X	X		Χ	Χ	Χ	Χ
Medical Screening Interview	X						
Anxiety and Related Disorders		X		X	Χ		
Interview Schedule-5 Specific Phobia							
Module							
Post-Dental Anxiety Intervention			X				
Debriefing Interview							
Post-Dental Appointment Debriefing			X				
Interview							
Pain Intensity Numeric Rating Scale			Х				
Pain Sensitivity Index		Х		Х	Х		
Anxiety Sensitivity Index-3		Х		Х	Х		
Distress Tolerance Scale		Х		Х	Х		
Fear Questionnaire Blood-Injury-		Х		Х	Х		
Injection Subscale							
PROMIS-Sleep Disturbance-Short	_	Х		Х	Х		
Form							

Page 11 of 28 Revision: May 12, 2023

PROMIS-Sleep-Related Impairment-	Х		Х	Х	
Short Form					
Sheehan Disability Scale	Х		Х	Х	
Client Satisfaction Questionnaire-8		Χ	Х	Х	

Initial Screening Measures

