Pain Intensity Numeric Rating Scale (PI-NRS). The PI-NRS is a widely utilized 11-point measure that assesses physical pain intensity on a scale ranging from 0 (no pain) to 10 (worst possible pain). The PI-NRS has been used to assess pain intensity in several studies conducted in medical settings (Farrar et al., 2001, 2010; Rowbotham et al., 2004; van der Roer, 2006). Anxiety increases subjective pain experience, and therefore this scale will be used to assess the intensity of dental related pain that participants experienced during their scheduled dental appointment and expect to experience at their next dental appointment. The PI-NRS will be administered as part of the post-dental-appointment debriefing interview.

Attendance at Dental Appointments

Given that avoidance of dental appointments is strongly connected to dental anxiety, we will also assess whether the Internet-based dental anxiety intervention increases attendance at future dental appointments. We will utilize TUKSoD's automated scheduling system (axiUm, http://www.axiumdental.com/) to do so. It is acknowledged that attendance may be influenced by factors unrelated to dental anxiety, but it is a reasonable hypothesis that anxious avoidance plays a role in attendance, and individuals with dental phobia are less likely to visit a dentist at least once a year than persons without. Thus, it is of interest to determine whether attendance at appointments scheduled prospectively after the index appointment is affected by treatment, and we will monitor this for the following 12-month interval. These data will not be collected for active control patients, who will be offered the intervention to be administered before their first scheduled dental appointment after the completion of the 3-month follow-up.

Planned Analyses

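### Aim 3's before/after attendance test is named as a one-sample chi-square on the same patients, with no paired method or unit stated, so its type I error is not guaranteed at 5%; the responder model counts attendance that may precede its predictor

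*Combined protocol and SAP*

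**What the plan says.** All three attendance analyses are in section 8c, Planned Analyses, Specific Aim 3.

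- **Before/after.** With both intervention groups combined, the overall attendance rate is compared "using a one-sample Chisquare test comparing the 12-month periods immediately before and immediately after the delivery of the intervention".
- **Between arms.** "We will also use a Chi-square test to compare post-intervention attendance rates between the two intervention groups." The plan adds: "We expect the attendance rates will be similar for the two groups."
- **Responder model.** Logistic regression is used for "predicting attendance/nonattendance among intervention patients who did or did not demonstrate reduction in dental anxiety at 3-month follow-up".

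The opening sentence of the Aim 3 section sets a 12-month follow-up for attendance. Follow-up Visits (Times 4 and 5) fixes the responder assessment: "Time 5 is the follow-up contact three months (12-15 weeks) after the day" of the intervention and dental appointment. Attendance at Dental Appointments describes the interest as whether "attendance at appointments scheduled prospectively after the index appointment is affected by treatment", and says of the comparison arm: "These data will not be collected for active control patients".

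The significance level of 0.05 is written under Aims 1 and 2. None is written under Aim 3.

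**The concern.** A one-sample chi-square compares an observed proportion with a known reference value, and the documents contain no such value. The obvious substitute is the observed pre-period rate. That choice treats an estimate as a constant and ignores that the same patients produced both rates. The first error makes the test reject too often. The second makes it reject too rarely when the two periods are positively correlated. The net effect depends on a correlation that the plan does not give.

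The unit is also open. An overall attendance rate can be a share of patients or a share of appointments. If appointments are counted, repeated visits by one patient are not independent, and the plan names no method for that. Nor does it define attendance for a patient who kept some appointments and missed others.

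The responder model has an ordering problem. Its predictor is known only at 12 to 15 weeks. Visits attended before then may themselves have lowered anxiety, so part of any association could run from attendance to anxiety reduction.

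Attendance is the third of the three primary objectives in section 4, and the before/after test is the only one of the Aim 3 analyses that tests for change over time. Analysts working in good faith could reach different conclusions from the same data.

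**Working it through.** The plan gives no rate, power or error figure for Aim 3, so there is nothing of its own to reproduce.

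**Inputs**
- Patients: section 8a gives about 550 over three roughly equal arms, so 550 × 2/3 ≈ 367 in the two I-CBT arms, before withdrawals.
- Assumed, because the documents are silent: 75% attendance, a two-sided 5% level, pre/post correlation ρ of 0.3 to 0.7, 2 to 4 appointments per patient per period, and within-patient correlation (ICC) of 0.1 to 0.3.

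**1. Patient as unit, observed pre-period rate as the null**

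One-sample statistic: z = (post − pre) / √[pre(1 − pre)/n]. Under no change, the true variance of the difference is 2(1 − ρ) times the variance used, so

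size = 2 × [1 − Φ(1.96 / √(2(1 − ρ)))].

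For an ordinary Pearson 2×2 that ignores pairing, the factor is (1 − ρ) instead of 2(1 − ρ). McNemar's statistic is (b − c)²/(b + c) on the discordant pairs.

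| ρ | One-sample, formula | One-sample, simulated | Pearson 2×2, simulated | McNemar, simulated |
|---|---|---|---|---|
| 0.3 | 9.8% | 9.8% | 1.9% | 5.0% |
| 0.5 | 5.0% | 5.2% | 0.6% | 5.1% |
| 0.7 | 1.1% | 1.2% | 0.0% | 5.0% |

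The simulation used 200,000 multinomial draws per setting with n = 367. At attendance of 60% or 90%, the one-sample size moves by at most 0.3 points.

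Simulated power for a change from 75% to 80%, at ρ = 0.3, 0.5 and 0.7, is 59%, 61% and 64% for the one-sample test and 49%, 63% and 85% for McNemar. The one-sample advantage at 0.3 comes from its inflated size. It clearly loses power only at 0.7.

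**2. Appointment as unit, observed pre-period rate as the null**

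The form is the same: size = 2 × [1 − Φ(1.96/√k)], where k is the true variance divided by the variance used.

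- Stable patient effect, equal counts: k = 2(1 − ICC). ICC 0.1 gives k = 1.8 and 14.4%; ICC 0.3 gives k = 1.4 and 9.8%.
- Stable effect, 2 appointments before and 4 after: k = 3(1 − ICC), giving 23.3% and 17.6%.
- Stable effect, 4 before and 2 after: k = 1.5(1 − ICC), giving 9.2% and 5.6%.
- Period-specific patient effect, m appointments in each period: k = 2[1 + (m − 1)ICC]. The lowest is 18.6% (m = 2, ICC 0.1) and the highest 31.5% (m = 4, ICC 0.3).

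The range is therefore about 6% to 31%. Beta-binomial simulation gave 5.7% to 31.6% over the same settings, and 4.7% to 5.3% for a patient-clustered paired test.

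**3. Responder model**

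If attendance is counted over the full 12 months, the share that precedes the predictor is 12/52 = 23% to 15/52 = 29%. The size of any resulting bias cannot be derived from the documents.

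**The case against.** The strongest reply is that the plan never says the pre-period rate is a fixed null value. The text describes one pooled group measured twice, and McNemar's test is a chi-square on that group's discordant pairs. For Aim 2 the authors write that "we will assess the differences between the interventions and control using two-sample" *t*-tests, so one-sample under Aim 3 may simply mean one group. They also plan paired *t*-tests for within-group change under Aim 1, which shows that they recognise pairing. This reading is possible and, if it is right, the size is about 5%. But the Aim 1 wording cuts both ways: where the authors mean a paired test they say so, and under Aim 3 they do not. The reply does not settle the unit either.

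It is also fair that every magnitude above rests on assumed inputs, and that 367 ignores withdrawals and patients without appointments in both periods. The figures show how much the open choices matter. They do not show a realised error.

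Four stronger readings are tempting, and the documents do not support them.

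- **That the test is simply anticonservative.** It may be above, at or below 5%, depending on the reading, the unit and the correlation.
- **That the before/after window is missing.** It is stated as 12 months on each side, and the opening sentence of Aim 3 gives 12 months for attendance generally.
- **That the index appointment inflates the after period.** Specific Aim 3 counts from delivery of the intervention and Attendance at Dental Appointments counts from after the index appointment. Section 8d treats that appointment as part of the intervention, which largely reconciles the two. A confirming phrase is enough.
- **That a non-significant between-arm chi-square will be taken as proof of similarity.** The plan states an expectation of similar rates and nowhere says it will draw that inference.

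**Conclusion.** The concern holds in a conditional form and should be fixed. The before/after test is under-specified: it has no reference rate, no named paired or clustered method and no stated unit. If the observed pre-period rate is used as the null, size is not guaranteed at 5%. It is about 10%, 5% and 1% at correlations of 0.3, 0.5 and 0.7 per patient, and about 6% to 31% per appointment. If McNemar's test was meant, there is no error to correct, only wording. These figures assume 367 patients, 75% attendance, a 5% level that Aim 3 does not state, and the correlations and appointment counts listed above.

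The responder model's overlap of 23% to 29% applies if the 12-month period at the head of Aim 3 is its window. It limits what the association can mean, by an unknown amount.

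A valid paired test would still leave the before/after result uncontrolled, because attendance is not collected in the control arm. The primary outcomes, MDAS and the ADIS-5 fear rating, are untouched.

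**What to change.** In Specific Aim 3:

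1. State the unit and the significance level, and replace the one-sample chi-square accordingly.
   - *Patient as unit:* define a yes/no outcome for patients with several appointments (for example, attended every scheduled appointment in the period) and use McNemar's test. The between-arm chi-square can stay.
   - *Appointment as unit:* use a logistic GEE clustered by patient, or a random-intercept logistic model, with period as a within-patient factor. Cluster the between-arm comparison by patient as well.
2. In the responder model, count only appointments after the 3-month assessment.
3. Confirm that the index appointment is not counted in the after period, in line with Attendance at Dental Appointments.
4. Report the before/after result as an uncontrolled change.

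The cost is plan wording and a few lines of code; attendance already comes from the scheduling system. There are three downsides. McNemar's test uses only patients with an outcome in both periods. A single yes/no per patient loses detail where there are several visits. Starting the responder count at the 3-month assessment drops the first 12 to 15 weeks of appointments from that model.
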